The two non-nicotine prescription medications, varenicline and bupropion, have not been considered for OTC status, in part because both had a 'box warning' placed on them by the FDA due to concerns that their use might cause or exacerbate psychiatric symptoms such as suicidal ideation or behavior. After multiple studies, including one of the largest smoking cessation trials ('EAGLES' study) ever conducted,¹⁷ it is clear that these medications do not cause statistically higher psychiatric adverse events than placebo or NRT. More specifically, in the EAGLES study, the FDA-approved dose of varenicline was found significantly more effective than bupropion, patch and placebo, and did not result in adverse events that necessitates a box warning, so the FDA removed the box warning. Thus, in combination with behavioral support, varenicline has the greatest probability of helping the most smokers quit with a similar adverse event profile to current OTC NRT products.

Given these data, the time has come to explore whether varenicline is safe and effective when no behavioral support is provided as a foundation to assessing whether it can be safe and effective as an over-the-counter medication. This is important because in real world use, smokers often do not receive behavioral support, so there is value in assessing whether varenicline quit rates will still be high without that behavioral support. Moreover, since the adverse events from varenicline have been shown to be comparable to the OTC nicotine patch, this research will assess whether varenicline, in two different doses, can be safe and effective without a healthcare provider prescription. More specifically, because earlier research found that .5mg twice a day (b.i.d.) varenicline is as effective as the currently FDA-approved 1.0mg b.i.d. dosing but with lower incidence of nausea and sleep disturbance⁶, there is value in assessing whether the lower dose will work as well as the higher dose in an OTC environment. Lastly, to understand the within-person mechanisms explaining *how* and *when* OTC varenicline might improve cessation outcomes, as well as how side effects affect medication adherence, we will also assess experience with OTC varenicline via ecological momentary assessment (EMA).

Primary Objectives

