- 1. To assess the safety and efficacy of the current FDA-approved 1 mg b.i.d. varenicline for smoking cessation in comparison with placebo when used in a simulated OTC study with no behavioral support provided.
- 2. To assess the safety and efficacy of .5mg b.i.d. varenicline in comparison with 1mg b.i.d. varenicline and placebo when used in a simulated OTC study with no behavioral support provided.

Secondary Objectives

- 1. To evaluate whether subject specific characteristics (e.g. socioeconomic status, ethnicity, smoking history, etc.) moderate primary (safety and efficacy) and secondary (adherence) outcomes.
- 2. To evaluate medication use patterns to assess whether varenicline is being used as indicated on the label, and to determine if medication adherence mediates cessation outcomes between-subjects.

3. In a subsample of participants, to examine how medication adherence, withdrawal, and side effects (e.g. nausea and sleep disturbance) vary within-subjects and are associated with smoking status using EMA in the first two critical weeks of medication use.

[figure not shown]
Hypotheses

- 1. Quit rates in the 1 mg b.i.d. varenicline condition will be significantly higher than the placebo medication condition when provided as an OTC medication.
- 2. Quit rates in the .5 mg b.i.d. varenicline condition will be comparable to the 1mg b.i.d. varenicline condition, and will be significantly higher than the placebo medication condition, when provided as an OTC medication.
- 3. Side effects will show a dose response relationship, with effects lowest in the placebo group.

C. EXPERIMENTAL METHODS Study Design

The primary objective of this study is to assess the efficacy of two different doses of varenicline used in a simulated OTC intervention relative to placebo (total N = 432). The design is a three-group placebo-controlled, double blind, block randomized clinical trial (as indicated in the figure), where participants will be randomly assigned to one of three

conditions: (1) 1 mg b.i.d. varenicline for 12 weeks, which is the current FDA-approved dose, (2) 0.5 mg b.i.d. varenicline for 12 weeks, or (3) placebo.

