Potential Risk. The most recent data found that varenicline does not result in greater risk than nicotine patch, which is already an over-the-counter medication, and that led the FDA to remove the box warning on varenicline. The most common side effects of varenicline are: nausea, sleep problems (trouble sleeping, vivid, unusual, or strange dreams), constipation, and gas and/or vomiting, and there is a very small risk that a participant could develop an allergic reaction to varenicline. In addition, the product warnings indicate that: "Some people have had new or worse mental health problems, such as changes in behavior or thinking, aggression, hostility, agitation, depressed mood, or suicidal thoughts or actions while taking or after stopping varenicline. These symptoms happened more often in people who had a history of mental health problems. Some people have had seizures during treatment with varenicline. New or worse heart or blood vessel problems can happen with varenicline. Sleepwalking can happen with varenicline, and can sometimes lead to harmful behavior.^{31"}

Participants might also experience withdrawal symptoms from quitting smoking, including urge to smoke, depressed mood, trouble sleeping, irritability, frustration, anger, feeling anxious, difficulty concentrating, restlessness, decreased heart rate, increased appetite or weight gain.

Protection Against Risks. Product information provided to participants will encourage them to use the product with a full glass of water after eating a meal. The product information will encourage use caution when using machinery or driving, and to

decrease alcohol consumption. In addition, information on symptoms associated with an allergic reaction will be provided. In addition, we will monitor participants at every visit to assess any potential adverse events, they will have a phone number that can be called at any time to contact study investigators, and they will be followed after they have discontinued medication to assess any effects for up to three months after medication completion.

Potential Benefits to the Subjects. The potential benefits to participants are substantial because it could help them to quit smoking, which is the leading preventable cause of death in the US.

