Adverse Event (AE) Definitions. Any negative event subsequent to signing consent but prior to the week 13 visit will be considered a potential adverse event to be addressed and followed, regardless of whether it is related to use of study medication. Examples of AEs include: (1) Clinical signs and symptoms, (2) Abnormal test results, (3) Worsening of existing medical conditions. The licensed medical professional (LMP) will consider adverse events serious if the event: (1) is life threatening, (2) results in death, (3) leads to incapacity, hospitalization, or serious impairment of normal life, (4) congenital abnormality or birth defect. Serious AEs will be reported to the IRB within 24 hours of the site becoming aware of the event. Once an adverse or serious adverse event is identified, it must be followed and recorded, such that subsequent to the designation each event

outcome should be characterized as follows: 1 = Still present, 2 = Resolved with Sequelae, 3 = Resolved without Sequelae, 4 = Lost to follow-up/Unknown, 5 = Death.

Determination of Severity. The study coordinators will make a determination of AE severity and provide a grade for each event according to the following criterion: Mild: Symptoms cause little discomfort, are easily tolerated, and do not significantly interfere with normal everyday activities. Moderate: Symptoms are uncomfortable and interfere with normal everyday activities. Severe: Symptoms cause significant impairment of everyday activities, incapacitation, or death

Determination of Causality. The LMP will make a determination the causality of each adverse event in relation to the study medication using the following criteria: 1 = Definite, 2 = Probable, 3 = Possible, 4 = Remote, 5 = Definitely Not

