Data Sharing Plan. The information that we will collect includes medically-related information that is protected and must remain confidential, so all standard methods to protect participant confidentiality will be employed, including maintaining information in password protected encrypted databases to reduce the risk of a data breach. Shared data across the two study sites will likewise be password protected and encrypted. After study completion, any outside requests for data will require a data sharing agreement that assures the following: (1) all data must be maintained in a secure fashion using appropriate technology, (2) commitment to use the data only for the research purposes requested, and (3) all shared data must either be destroyed or returned, including written assurances to that effect.

Statistical Analysis Plan

Main study. The participation flow will be reported following CONSORT guidelines. Intention to treat analysis will be applied for all statistical analyses. The data collected from the study will be summarized by the descriptive statistics for overall and by treatment condiction (1mg b.i.d., .5mg b.i.d. and placebo) and by the application of EMA (yes/no). The primary analysis will include estimating and comparing the guit rates between treatment arms. We will fit a logistic regression to model the probability of smoking cessation at 12 weeks with treatment condition, application of EMA and the interaction term of the two main effects as independent variables. If the interaction term is not significant, this implies the guit rates for the same treatment condition are similar in those with and without the utilization of EMA, and we will drop the interaction term and fit a model with main effects only. The comparison will be perfromed by the Wald test from the logistic regression with Bonferroni adjustment to account for multiple comparisons. The point estimate of guit rate and 95% confidence interval (CI) for each treatment condition will be reported. If the interaction term is significant, we will conduct the comparisons in EMA and non-EMA subgroups. A similar approach will be applied to the analysis of adherence and adverse events. These two outcome variables can be analyzed as a dichotomous (yes/no) or count variable (pill count and number of adverse events), and the logistic regression and Poisson regression will be used to evaluate whether group differences occur. In the secondary analysis, to evaluate

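### Hypothesis 3 concerns drug side effects, chiefly nausea and sleep disturbance, but the main-study analysis tests adverse events only as all-cause yes/no or total count

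*Combined protocol and SAP*

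**What the plan says.** Both primary objectives cover safety as well as efficacy. Hypothesis 3 reads: "Side effects will show a dose response relationship, with effects lowest in the placebo group". Specific Aims justifies the lower dose by earlier work that found similar efficacy "but with lower incidence of nausea and sleep disturbance".

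The Statistical Analysis Plan (Main study) handles adverse events in two sentences. The first is "A similar approach will be applied to the analysis of adherence and adverse events", where the approach meant is the quit-rate analysis: logistic regression with an EMA term and Bonferroni-adjusted Wald tests. The second says that adherence and adverse events "can be analyzed as a dichotomous (yes/no) or count variable (pill count and number of adverse events", with logistic or Poisson regression. It names no symptom, no post-dose subset and no drug-related subset.

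Adverse Event (AE) Definitions sets the scope: "Any negative event subsequent to signing consent but prior to the week 13 visit will be considered a potential adverse event", and this applies "regardless of whether it is related to use of study medication". Determination of Causality adds that "The LMP will make a determination the causality of each adverse event in relation to the study medication", on a five-level scale. No stated analysis uses that rating.

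Two other parts of the plan bear on the point. Withdrawal has its own instrument, the MNWS, at baseline and every scheduled follow-up contact. The EMA sub-study records nausea, sleep quality and vivid dreams in 25 participants per arm for two weeks. Its H1 concerns these symptoms over the first week, and its H2 expects the largest within-person change at 1 mg b.i.d.

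**The concern.** The hypothesis and the tested outcome are different quantities. Hypothesis 3 is about effects of the drug. The outcome is any untoward event, or the total number of them, from consent to week 13. Colds, injuries and events before the first dose all count. The pre-dose interval is not trivial in the remote cohort, where participants have 30 days from the first screening visit to begin medication. Events unrelated to the drug occur about equally in all arms. They shrink the difference in proportions and add variance to the counts.

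The main case for the lower dose is its tolerability. A diluted comparison pushes towards finding no significant difference in adverse events. In a trial meant as groundwork for over-the-counter use, that result could be read as reassurance when it partly reflects the choice of outcome.

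**Working it through.** **The plan's own figure.** Sample Size gives 110 per group for 23% vs 8% at 0.025 with at least 80% power. It has no calculation for adverse events in the main study. The formula is

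power = Φ{[d√n − z√(2p̄(1−p̄))] / √[p₁(1−p₁) + p₀(1−p₀)]}, where d = p₁ − p₀ and p̄ is the mean of p₁ and p₀.

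With d = 0.15, n = 110, p̄ = 0.155 and z = 2.241: (1.573 − 1.147)/0.501 = 0.851, and Φ = 80.3%. The stated figure reproduces, and the same formula is used below.

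**Inputs.**
- From the documents: 432 randomized 1:1:1, so 144 per arm.
- Assumed, because the documents give no rates: nausea 10/20/30% for placebo/0.5 mg/1 mg; independent background events in b = 30, 50 or 70% of every arm; two-sided 0.05.
- Two scenarios: (A) only nausea differs by arm; (B) sleep disturbance, independent of nausea, also runs 10/20/30%.

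**Any-event risk.** Under A it is 1 − (1−b)(1−nausea). Under B it is 1 − (1−b)(1−nausea)(1−sleep). Example under A with b = 50%: placebo 1 − 0.5×0.9 = 55%, 1 mg 1 − 0.5×0.7 = 65%. Power: (0.10×12 − 1.96×0.693)/0.689 = −0.229, Φ = 41%.

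| Background b | A: any-event rate, placebo / 0.5 / 1 mg | A: power, 1 mg vs placebo | A: power, 0.5 mg vs placebo | B: any-event rate, placebo / 0.5 / 1 mg | B: power, 1 mg vs placebo | B: power, 0.5 mg vs placebo |
|---|---|---|---|---|---|---|
| 30% | 37 / 44 / 51% | 67% | 23% | 43 / 55 / 66% | 97% | 52% |
| 50% | 55 / 60 / 65% | 41% | 14% | 60 / 68 / 76% | 83% | 32% |
| 70% | 73 / 76 / 79% | 22% | 8% | 76 / 81 / 85% | 54% | 18% |

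Nausea as its own outcome has 99% power for 30% vs 10% and 66% for 20% vs 10%.

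**At 0.025.** The adverse-event analysis borrows the Bonferroni approach. Nausea alone then has 98% (1 mg) and 55% (0.5 mg). Any-event power for 1 mg is 56/30/15% under A and 95/75/43% under B. For 0.5 mg it is 15/8/5% under A and 41/23/12% under B.

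**Low background.** With b = 20% at 0.05, any-event power for 1 mg is 81% under A and 99% under B. For 0.5 mg it is 31% under A and 65% under B. If background events are that rare and both symptoms differ, almost nothing is lost relative to nausea alone.

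**Total count, 1 mg vs placebo.** Power = Φ{δ/√[(μ₁+μ₀)/144] − 1.96} with ideal Poisson variance. Under A with one background event per person, μ = 1.1 vs 1.3: 0.2/√(2.4/144) = 1.549, power 34%. With two background events it is 21%. Under B (δ = 0.4) the figures are 82% and 59%.

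**The EMA sub-study as a substitute.** A simple comparison of 30% vs 10% with 25 per arm has 31% power at 0.025 (42% at 0.05). The 80% in Sample Size for EMA refers to day 5 against day 1 odds, not to a difference between arms.

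**The case against.** The strongest reply is that the plan does analyse these symptoms: the EMA sub-study measures nausea, sleep and dreams directly and has a dose hypothesis. That stands as far as it goes. A reader might infer that the nausea and sleep signal is analysed nowhere, and that would be wrong. But 25 per arm for two of twelve weeks, powered for change within person, does not test Hypothesis 3 in the randomized sample.

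A second reply is that the adverse-event definition is a rule for capture and follow-up, and that the SAP wording is permissive, so models by symptom are not ruled out. This is correct. What remains is that they are not specified, and a symptom picked after the data are seen carries less weight than one named now.

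A third concerns withdrawal. A reader might infer that withdrawal symptoms are counted as adverse events and bias the comparison. No sentence says so, the MNWS scores withdrawal separately, and any bias could run either way because both quitting and relief of withdrawal may differ by arm. What stands is narrower. Potential Risk lists sleep problems among the drug's side effects and then says "Participants might also experience withdrawal symptoms from quitting smoking, including urge to smoke, depressed mood, trouble sleeping, irritability". No rule says how a sleep complaint is to be classed.

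Finally, power figures in which only nausea differs overstate the loss, since an any-event outcome also collects sleep disturbance. This is right, and scenario B shows it. All-cause events are also a legitimate safety outcome and should not be dropped.

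**Conclusion.** The concern holds as a mismatch between hypothesis and outcome: apart from the small EMA sub-study, no stated analysis compares nausea or sleep disturbance between arms. How much this costs depends on event rates that the documents do not give. Over background rates of 30-70%, the loss for 1 mg vs placebo ranges from slight (97% against 99%) to severe (22% against 99%). For 0.5 mg vs placebo it is marked throughout (8-52% against 66%), though it nearly vanishes at 20% background if both symptoms differ. The calculation also assumes independent events and all 144 per arm. The plan to analyse the in-person and remote cohorts separately first would lower every figure.

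A reader might conclude that the trial is likely to report no difference in adverse events even if nausea differs threefold. The documents do not support that as a forecast, because it fails under scenario B at low or moderate background.

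Naming the outcomes does not make every comparison strong. On the assumed rates, nausea at 1 mg vs 0.5 mg (30% vs 20%) has 50% power at 0.05 and 39% at 0.025.

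**What to change.** In the Statistical Analysis Plan (Main study):

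1. Name the Hypothesis 3 outcomes as the incidence after first dose of (a) nausea and (b) sleep disturbance including abnormal dreams. Each is yes/no per participant, in all randomized participants, analysed with the logistic model already planned.
2. State one rule, applied blind to arm, for classing sleep complaints that could be withdrawal.
3. Add, as a supportive outcome, any event that the blinded licensed medical professional rates Definite, Probable or Possible.
4. Keep the any-event and total-count analyses alongside as the all-cause safety summary.

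No new visits or measurements are needed. The cost is SAP wording, coding of recorded event terms, and a short multiplicity statement, because there will be two or three safety outcomes instead of one. The text available shows no adverse-event form or coding dictionary, so the coding effort should be confirmed before the change is adopted.

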Alternatives to Participation. Any of those who are not eligible for the study will be referred to the free smoking cessation quitline available in both states. In addition, any participants who elect to drop out of the study will also be referred to the state quitline, or could potentially obtain Chantix or another medication from their healthcare provider.

Investigational Product

Product: Varenicline (generic name, product name is Chantix™)

Doses: 0.0 mg, .5mg and 1.0 mg

Product Form: Pill

Product Administration: Oral, with water

Manufacturer: Pfizer

Varenicline and Placebo. In this study, participants will be randomly assigned in double-blind fashion to use one of two doses of varenicline (.5 mg b.i.d. or 1.0mg b.i.d.) or placebo (see study design above). Both varenicline and the placebo will look identical and be in identical packaging.

Medication Dosing. Participants assigned to the 1.0 mg b.i.d. condition, which is the current FDA-recommended dosing, will follow the recommended varenicline titrated dosing schedule as follows: days 1 through 3: 0.5mg, one daily; days 4 through 7: 0.5mg, twice daily; days 8 through end of treatment: 1mg, twice daily. Those assigned to the 0.5mg bid. condition will begin use 0.5mg once daily days 1 through 3, then will begin using 0.5 b.i.d on day 4 through the end of the study. Those assigned to the placebo condition will use pills that look identical to those that are being used in the other conditions but contain no medication. The subjects in the placebo group will also titrate during the first 7 days (1 pill days 1-3, 2 pills for the duration of the treatment period). All participants will take identical looking pills at the same time throughout the study, with the only difference being the amount of varenicline included in each pill.

Product Packaging. Medication packaging for this study will be implemented at the ASU site. Two study staff will work together to package the medications, and all packaging will be double checked and tracking forms maintained by the staff to assure quality control. Medications will be shipped by FedEx or equivalent to LACT (or directly to participants if they are participating in the study remotely), where study product will be checked and a report provided back to ASU within 24 hours indicating whether all sent medications were received.

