the impact of participant characteristics on the study outcomes, we will fit multivariable logistic or Poisson regression models. The odds ratio (from logistic regression) and ratio or percent change (from Poisson regression) will be reported to quantify the association.

In addition to evaluting the primary and secondary outcomes at the end of treatment (12 week), the trend over time between the initiation of treatment and at the end of the follow up period is also of interest. We will implement generalized linear mixed model (GLMM) with random intercept to account for the clustering effect (multiple visits clustered within each participant). Independent variables will include treatment condition, visit number, and other time-varying characteristics collected post radomization. We intend to use two-level GLMMs, and will perform exploratory analysis using 3-level GLMMs (visits clustered within participants, and participants clustered within sites [CA, AZ]), as we anticipate the variability from sites would be negligible.

Analysis of the Remote Cohort. We will assess the in-person and remote cohort data via separate analyses, but because the fundamental study design in the same for both, if the outcomes of the separate analyses suggest similar outcomes, we might combine the results of both groups into a single analysis.

EMA Statistical Analysis Plan. Our approach to analyzing EMA data is based on published approaches^{32,33} using GLMMs. This class of models is useful for analyzing EMA data because they allow multiple observations per subject, multiple levels of nesting (i.e., observations within weeks within subjects), multiple subject random effects, modeling of between-subjects (BS) and within-subjects (WS) variance as a function of time-invariant covariates (e.g. treatment assignment, gender, or nicotine dependence), and extension to non-normal outcomes (i.e., dichotomous, ordinal, counts). Our primary approach will be a three-level mixed model treating observations (level 1) within days (level 2) within subjects (level 3). Additionally, we will employ a time-varying effect model (TVEM)³⁴ if we find evidence that the relative association between momentary medication adherence, side effects, craving, and smoking varies over the two weeks of observation.³⁵ We present brief examples of analyses of central interest below.

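### Poisson regression is named for pill counts and adverse event counts with no dispersion or robust-variance provision, so its ordinary standard errors are right only if variance equals mean

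*Combined protocol and SAP*

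**What the plan says.** The primary quit-rate analysis is a logistic regression with Wald tests and a Bonferroni adjustment. The plan then states: "A similar approach will be applied to the analysis of adherence and adverse events". On the form of these outcomes it says: "These two outcome variables can be analyzed as a dichotomous (yes/no) or count variable". For the count form, the model named is Poisson regression; the full wording is a "count variable (pill count and number of adverse events), and the logistic regression and Poisson regression will be used to evaluate whether group differences" occur.

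Poisson regression is named again in the secondary analysis of participant characteristics, where "we will fit multivariable logistic or Poisson regression models". The resulting ratios or percent changes are to be reported.

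Neither place mentions over-dispersion, a scale parameter, a negative binomial model or a robust variance. Two nearby provisions might seem to help but do not reach this comparison. The random-intercept GLMM is added for trends over visits, on top of the week 12 evaluation. The modelling of between- and within-subject variance concerns the EMA data only.

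The outcomes matter to the trial. Both primary objectives include safety, and Secondary Objective 1 asks whether participant characteristics "moderate primary (safety and efficacy) and secondary (adherence) outcomes". Hypothesis 3 predicts: "Side effects will show a dose response relationship".

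**The concern.** A Poisson model fixes the variance at the mean, and its default standard errors inherit that. Neither count has a reason to obey it. A pill total is bounded by the schedule and driven by how consistently each person takes the medication and when they stop. Adverse event counts commonly vary more between people than Poisson allows.

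If the true variance exceeds the mean, intervals are too narrow and differences between arms are declared too often. If it is smaller, intervals are too wide and real differences are missed. Interval coverage suffers as well as the false-positive rate, so the problem remains even if side effects do rise with dose. The same standard errors would feed the moderator models under Secondary Objective 1.

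**Working it through.** **The plan's own figure.** The plan states no figure for the count analyses. Its only main-study calculation is for quit rates: 23% vs 8%, alpha 0.025, 80% power, 110 per group. A two-sided test with pooled variance and no continuity correction gives 110 per group and 80.3% power. That figure reproduces and is not affected here.

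**Inputs from the documents**
- Medication Dosing gives the placebo schedule as "1 pill days 1-3, 2 pills for the duration of the treatment period"; the active arms also take one pill daily for three days and then two. Over 84 days: 3 + 81 × 2 = 165 pills.
- Table 2 puts the week 12 target at day 98. Read that far: 3 + 95 × 2 = 193 pills.
- One 28-day interval at two pills a day: 56 pills.
- Total N is 432, randomised 1:1:1, so 144 per arm.

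**Assumptions.** The documents give no mean, SD or dispersion for either count. Every spread below is assumed.

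**Formulas**
- Poisson SE of a log ratio between two arms with totals S₁ and S₂: √(1/S₁ + 1/S₂).
- If variance = φ × mean, the true SE is √φ times that. Type I error at nominal 5% is 2 × [1 − Φ(1.960/√φ)], and the Poisson interval is 1/√φ times the correct width.
- For P scheduled pills, mean adherence m and SD s (as proportions): φ = P × s²/m. Variance equals mean at s = √(m/P).

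**Where Poisson is right.** At m = 65%, 80% and 90%, the required SD in percentage points is 6.3, 7.0 and 7.4 for 165 pills; 5.8, 6.4 and 6.8 for 193; and 10.8, 12.0 and 12.7 for 56.

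**Pill count, m = 80%, nominal 5%**

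| SD (points) | φ, 165 pills | Width ratio | Type I, 165 | Type I, 56 | Type I, 193 |
|---|---|---|---|---|---|
| 5 | 0.52 | 1.39 | 0.6% | <0.1% | 1.2% |
| 7 | 1.01 | 0.99 | 5% | 0.1% | 7% |
| 10 | 2.06 | 0.70 | 17% | 1.9% | 21% |
| 20 | 8.25 | 0.35 | 50% | 24% | 53% |
| 30 | 18.56 | 0.23 | 65% | 43% | 67% |

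**Direction.** Take mean use 95%, SD 4 points, and 10% of people stopping at a uniformly random time, with 165 pills scheduled.
- Stoppers counted low: mean = 0.9 × 0.95 + 0.1 × 0.475 = 0.9025; SD about 17 points; φ = 5.36; type I error about 40%.
- Stoppers' counts missing: φ = 165 × 0.04²/0.95 = 0.28; type I error 0.02%.

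**Adverse event counts.** φ = 1.5, 2 and 3 give type I error of 11%, 17% and 26% at nominal 5%.

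**Simulation** (20,000 replicates; beta-distributed adherence × 165; negative binomial adverse event counts with mean 2)
- Poisson at 144 per arm: pills 0.7%, 5.4%, 17.2%, 50.0% and 64.2% for the five SDs; adverse events 10.8%, 16.5% and 25.9%. These agree with the formula.
- Robust variance at 40, 72 and 144 per arm: 4.8–6.4%, 5.0–5.9% and 5.0–5.4%.
- Coverage of a nominal 95% interval at a true adverse event rate ratio of 1.5 (means 2 and 3): Poisson about 89%, 83–84% and 74%; robust 94.0–94.9%.
- Coverage for mean adherence 80% vs 72% at SDs of 5, 10, 20 and 30 points: Poisson about 99%, 81–82%, 49–50% and 33–34%; robust 94.4–95.1%.

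**The case against.** The strongest reply is that the plan names a model, not a variance estimator. Poisson regression with a sandwich variance is still Poisson regression, so nothing written is strictly false. This is fair: the gap is an omission. But ordinary standard errors are the natural reading of an unqualified Poisson model, and leaving the choice until the data are seen is an avoidable analyst decision.

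Further points:
- **The yes/no form is unaffected and the count form is optional.** True. The problem applies whenever the count form is used.
- **Bonferroni may carry over, making the nominal level 2.5%.** Possible. The 165-pill figures then become about 0.2%, 2.6%, 12%, 44% and 60%, and the adverse event figures 6.7%, 11% and 20%. The relative distortion remains.
- **The size is wholly assumed, and near φ = 1 the error is trivial.** Correct. This is why a variance that is valid either way is preferable.
- **Some scenarios fit loosely.** The first 28 days with titration schedule 3 + 25 × 2 = 53 pills, not 56 (at SD 20 points, φ = 2.65 and type I error 23% instead of 24%). The day-98 reading sits awkwardly with a 12-week supply. Wholly missing counts are less likely in person, where medication is retrieved at weeks 4, 8 and 12, than in the remote cohort, which returns it only at week 12. The 165-pill and adverse event results do not depend on these.
- **The GLMM absorbs some extra variation.** Only in the trend analysis.

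**Conclusion.** The concern holds. If the plan is followed with ordinary Poisson standard errors, comparisons of pill and adverse event counts are correctly calibrated only when variance happens to equal the mean, and nothing in the documents supports that.

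Neither the size nor the direction can be established from the documents. Over the assumed spreads, type I error at nominal 5% runs from below 0.1% to 67% for pill counts, depending also on how the total is read. For adverse events it is 11% to 26% at variance-to-mean ratios of 1.5 to 3.

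No count test is called primary or powered, and quit rates and sample size are untouched. This is a worthwhile, inexpensive improvement to the secondary and safety analyses.

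**What to change.** Keep the planned models and state in the Statistical Analysis Plan that every Poisson comparison of pill counts and adverse event counts will use a robust (sandwich) variance for tests and confidence intervals. This should cover the arm comparisons, the participant-characteristic models and, if the approach used for quit rates carries over, the test of interaction with EMA participation.

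The cost is a few words and one variance option in the same software, with no new data. There are two downsides:
- Intervals will be wider when counts are over-dispersed, as they should be.
- The robust test is slightly liberal in small groups. For the EMA interaction at nominal 5%, simulated type I error is 4.8–7.7% with 25 EMA participants per arm. The plan also says: "We will assess the in-person and remote cohort data via separate analyses". If one cohort then has only about 12 EMA participants per arm, the range is 5.1–10.1%, or 4.1–8.7% with an n/(n−1) correction.
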